12.7.2 Criteria for Suspending or Stopping Overall Study

Stopping criteria for Phase 2 will be determined by an independent DSMB, who will assess the specific event rates for DKA and severe hypoglycemia from the study at specific timepoints relative to published rates from large, population-based datasets. Stopping rules may be modified for the Phase 3 extension.

In consideration of adverse events rates occurring in this proposed study, the rates will be assessed relative to published rates from Foster et. al.¹⁰ and Miller et. al.²⁶ to determine whether severe hypoglycemia or diabetic ketoacidosis are within expected rates during this study. **Table 5: T1D Exchange Rates of Severe Hypoglycemia and Diabetic Ketoacidosis^{10,26}** provides a summary of these published rates.

Table 5: T1D Exchange Rates of Severe Hypoglycemia and Diabetic Ketoacidosis^{10,26}

Adverse Event	Frequency of subjects to experience ≥ 1 event extrapolated from T1DX registry 2016-2018, 2013-2014
Severe hypoglycemia (loss of consciousness or seizure)	4-5% < 18 years 7% ≥ 18 years

Diabetic ketoacidosis (overnight hospitalization)	3-4% < 18 years 2-3% ≥ 18 years
--	------------------------------------

For unanticipated adverse device effects (UADEs), the DSMB will determine whether the study should proceed or not based upon risk of additional serious adverse events and the underlying root cause analysis of the UADE.

Study activities could be similarly suspended if the manufacturer of any component of the investigational study device requires stoppage of device use for safety reasons (e.g. product recall).

The affected study activities may resume if the underlying problem can be corrected by a protocol or system modification that will not invalidate the results obtained prior to suspension.

The study Medical Monitor will review all adverse events that are reported during the study, and the DSMB will review all cases of severe hypoglycemia, DKA and UADEs as well as compiled safety data at periodic intervals. The Medical Monitor and/or DSMB may recommend suspension of study activities or stoppage of the study to the Sponsor if deemed necessary based on the totality of safety data available.

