12.3.3 Hypoglycemic Events

Hypoglycemia is only reportable as an adverse event when one of the following criteria is met:

- Severe Hypoglycemia: The event required assistance of another person due to altered consciousness, and required another person to actively administer carbohydrate, glucagon, or other resuscitative actions²⁵. This means that the participant was impaired cognitively to the point that he/she was unable to treat himself/herself, was unable to verbalize his/her needs, was incoherent, disoriented, and/or combative, or experienced seizure or

loss of consciousness. These episodes may be associated with sufficient neuroglycopenia to induce seizure or loss of consciousness. If plasma glucose measurements are not available during such an event, neurological recovery attributable to the restoration of plasma glucose to normal is considered sufficient evidence that the event was induced by a low plasma glucose concentration.

- Hypoglycemia resulting in an SAE that may not otherwise meet the definition of Severe Hypoglycemia defined above.

When a hypoglycemic event meets the above reporting requirements, an Adverse Event Form should be completed. A severe hypoglycemia event should be considered a serious adverse event and follow the SAE reporting requirements.

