12.3.4 Hyperglycemic/Ketotic Events

Hyperglycemia is only reportable as an adverse event when any of the following criteria is met:

- The event involved DKA, as defined by the Diabetes Control and Complications Trial (DCCT)²⁴ and described below
- Evaluation or treatment was obtained at a health care provider facility for an acute event involving hyperglycemia or ketosis, or the participant contacted the site and received guidance on how to manage the hyperglycemia/ketosis
- Prolonged hyperglycemia: defined as meter BG \geq 300 mg/dL and ketones $>$ 1.0 mmol/L
- Hyperglycemia resulting in an SAE that may not otherwise meet the above criteria

Hyperglycemic events are classified as DKA²⁴ if all of the following are present:

- Symptoms such as polyuria, polydipsia, nausea, or vomiting;
- Serum ketones $>$ 1.5 mmol/L or large/moderate urine ketones;
- Either arterial blood pH $<$ 7.30 or venous pH $<$ 7.24 or serum bicarbonate $<$ 15; and
- Treatment provided in a health care facility

When a hyperglycemia/ketotic event meets the above reporting requirements, Adverse Event Form should be completed.

Events meeting DKA criteria should be considered a serious adverse event and follow the SAE reporting requirements. Hyperglycemia events not meeting criteria for DKA generally will not be considered as serious adverse events unless one of the SAE criteria above is met.

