2.4 STUDY SUCCESS

The study will be deemed successful if the incidence rates of severe hypoglycemia and diabetic ketoacidosis during Phase 2 are considered acceptable compared to published rates.

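### The trial's severe hypoglycemia definition is wider than the Table 5 comparator and its DKA definition differs in both directions, yet no matched count is planned

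*Protocol*

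**What the plan says.** **Trial definitions.** Protocol 12.3.3 counts an event as severe hypoglycemia when altered consciousness made another person's help necessary and that person actively gave treatment. It spells this out to include a child who "was unable to verbalize his/her needs, was incoherent, disoriented, and/or combative", as well as seizure or loss of consciousness. Protocol 12.3.4 classifies an event as DKA only if four things are all present: symptoms, raised ketones, low pH or bicarbonate, and "Treatment provided in a health care facility".

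**Comparator.** Table 5 in Protocol 12.7.2 gives the share of registry subjects with at least one event. One row is "Severe hypoglycemia (loss of consciousness or seizure", with "4-5% < 18 years 7% ≥ 18 years". The other is "Diabetic ketoacidosis (overnight hospitalization", with "3-4% < 18 years 2-3% ≥ 18 years".

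**Use.** Section 12.7.2 states: "In consideration of adverse events rates occurring in this proposed study, the rates will be assessed relative to published rates", and names the two registry publications behind Table 5. SAP 2.4 calls the study successful if the Phase 2 rates "are considered acceptable compared to published rates"; Protocol 13.2 says the same in substance. SAP 5.4 proposes no formal safety test, and neither document sets a numeric limit. Protocol 12.9 and SAP 5.1 list what the Medical Monitor adjudicates (relatedness, category, seriousness, severity, anticipated or not). Whether an event meets the registry definition is not on the list.

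**The concern.** A comparison with an external rate is sound only if both sides count the same event. Here they do not, and the comparison carries weight: it informs the DSMB's stopping assessment and, through the phrase on published rates, the claim of study success. With around one event expected in Phase 2 on an annual reading of Table 5, one or two events that the registry label would not count could change how the result is read. Converting Table 5 to events per person-month would not cure this, because the numerators would still differ.

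**Working it through.** **Severe hypoglycemia, side by side.** A child who is combative and is given glucagon, but neither seizes nor loses consciousness, counts under 12.3.3 and not under the Table 5 label. Seizure and loss of consciousness are named in both. The comparator event is therefore in substance a subset of the trial event, and the direction is clear: the trial counts at least as many.

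**DKA, side by side.** A child meeting all four criteria who is treated in an emergency department and sent home counts in the trial and not under the Table 5 label. A child kept overnight with a DKA diagnosis who misses one of the 12.3.4 criteria may count under the label and not in the trial, since Table 5 shows no biochemical criteria. The net direction cannot be read from the documents.

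**Arithmetic, for illustration.** Table 5 cannot be re-derived: it is described as extrapolated from outside registries and states no observation window.

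Inputs from the documents: *p* = 4-5% (Table 5, under 18 years); *n* = 60 evaluable to 80 enrolled (Protocol 13.2); Visit 13 at day 94 (Table 1). Assumptions: the Table 5 window (12 or 3 months); *k*, the ratio of trial-definition to registry-definition events; and each cut-off.

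1. *Annual window, expected events.* Person-years = *n* × 94/365.25 = 15.44 (*n* = 60) or 20.59 (*n* = 80). Annual rate = −ln(1 − *p*) = 0.0408 or 0.0513. Expected registry-definition events λ = 15.44 × 0.0408 = 0.63 up to 20.59 × 0.0513 = 1.06.
2. *Chance of two or more events*, Poisson: 1 − e^(−kλ)(1 + kλ). At λ = 0.630 and *k* = 1: 1 − e^(−0.630) × 1.630 = 13.2%.

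| *k* | P(2 or more), lowest to highest λ |
|---|---|
| 1 | 13.2-28.5% |
| 1.5 | 24.4-47.0% |
| 2 | 35.9-62.4% |
| 3 | 56.4-82.5% |

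3. *Same window, another cut-off.* With *p* = 5% converted to a quarter year, risk = 1 − 0.95^(k/4) = 1.27%, 1.91%, 2.53% for *k* = 1, 1.5, 2. The exact binomial chance of 3 or more of 60 is 4.1%, 10.7%, 19.4%.
4. *Three-month window.* Risk = 1 − 0.95^k = 5.0%, 7.4%, 9.75%. The chance that more than 5% of 60 children (4 or more) have an event is 35%, 66%, 85%.
5. *Annual figure used without conversion.* If the raw 13-week percentage is set against an annual 5%, the chance of 4 or more of 60 is 0.7%, 2.8%, 6.6% for *k* = 1, 1.5, 2. An unconverted window would favor the device by more than the definition works against it; *k* would have to be about 4 to return to 35%.
6. *DKA.* With a three-month window and *p* = 4%, the chance of exceeding 4% of 60 (3 or more) is 12% if the trial criteria capture half the registry-type events, 43% if they capture the same number, and 70% if they capture 1.5 times as many.

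Once both sides are on one time base, the definition effect is material under either window. Its size depends on *k* and on the cut-off, and the documents give neither.

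**The case against.** A reader might infer that both events are defined more widely than in Table 5 and that the device will therefore look unsafe. The documents do not support that. For DKA, the joint symptom and laboratory criteria may outweigh the wider care setting. For the comparison as a whole, other mismatches act alongside the definitions:

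- The exclusion criteria remove children with severe hypoglycemia in the past 6 months, and DKA in that period with stated exceptions. This lowers the expected trial rates.
- The comparator is everyone under 18, not ages 2.0-5.9.
- Table 5 gives no window.

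Nor is any percentage above the probability of a planned decision. No threshold exists, and the two-event cut-off is arbitrary.

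The process is also not a mechanical count. The DSMB is told of every severe hypoglycemia and DKA case, may convene after any of them, and weighs the totality of safety data. The final stopping rules sit in a charter that is not among these documents and may specify how events are counted. Study success is tied to published rates in general; Table 5 is named only in the stopping section, so that link is an inference, though a natural one. Finally, a narrower count used alone could make a safety comparison in preschool children too lenient.

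All of this limits the claim and does not remove it. Offsetting errors of unknown size do not make unlike counts comparable, and a DSMB using judgment is helped by a matched count. The point on leniency is a reason to show the matched count beside the full one, not in its place.

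**Conclusion.** The point holds in a limited form. For severe hypoglycemia, the trial definition is wider than the Table 5 comparator. Other factors equal, the comparison with published rates runs against the device. This follows from the two texts and needs no assumption. For DKA, the definitions differ in both directions and the net effect is unknown. The overall bias is undetermined because of the exclusions, the age range of the comparator and its unstated window.

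The figures are illustrative. Under an annual reading and a two-event cut-off, *k* = 1.5 to 3 moves the chance of two or more events from 13.2-28.5% to between 24.4% and 82.5%, with no true excess. Other windows and cut-offs give quite different values. The defect to correct is that neither document plans a count on the comparator's definition. It should be corrected before Phase 2 results are reviewed, since re-classifying events afterwards would look post hoc.

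**What to change.** Keep the 12.3.3 and 12.3.4 definitions for the primary safety endpoints and for DSMB notification. In Protocol 12.7.2, SAP 2.4 and SAP 5.4, state that the comparison with Table 5 will show, next to the full-definition rates:

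- severe hypoglycemia events with seizure or loss of consciousness, as the like-for-like count;
- DKA events with overnight hospitalization, as the nearest available match, stating that the trial's symptom and laboratory criteria still apply and may differ from the registry's.

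Have the Medical Monitor flag both features at adjudication. These events are already adjudicated under Protocol 12.9, and 12.5 already asks for discharge summaries when a subject is hospitalized, so the information should usually be at hand. The cost is a sentence in each of the three places, two flags on the adjudication form and two extra table rows. The change does not resolve the window, age or exclusion mismatches, so the matched counts should not be presented as making the comparison unbiased.

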12.8 Data Safety Monitoring Board (DSMB)

The DSMB will be established prior to the first enrollment and consist, at a minimum, of two physicians and one statistician independent from the Sponsor and study. The physicians will have relevant therapeutic and medical expertise. The DSMB will determine the stopping criteria for Phase 2 of the study and review Severe Hypoglycemia and DKA as well as compiled safety data at periodic intervals to determine if the stopping rules apply. Stopping rules may be modified for the Phase 3 extension.

Compiled safety data may include listings of protocol deviations, device deficiencies, subject terminations, and subject withdrawals related to device or procedure safety. In addition, the DSMB members will be notified upon the occurrence of any UADEs to determine whether the study should proceed or not based upon risk and may request an ad hoc meeting to discuss. The DSMB will meet approximately every 6 months after the start of enrollment. The DSMB will also be requested to indicate whether or not they would like to conduct a review meeting after the notification of any events of Severe Hypoglycemia or Diabetic Ketoacidosis. If the DSMB requests a review meeting, one will be scheduled as soon as possible. Additional reviews may be conducted at any time based on the request of the DSMB, Sponsor or Medical Monitor. At the conclusion of each meeting, the DSMB will make a recommendation to the Sponsor concerning the continuation, modification, and/or termination, of the study and/or a statement regarding their overall assessment of device safety and continuation of the pivotal study. The final decision regarding the continuation, modification or termination of the study will reside with the Sponsor. Responsibilities, qualifications, membership and committee procedures, including the final stopping rules, will be outlined in the DSMB Charter.

12.9 Medical Monitor

An independent Medical Monitor will be responsible for individual and timely review of adverse events as defined below. The Medical Monitor will be a physician with relevant therapeutic and medical expertise that is not participating as an Investigator in the study and does not have a financial, scientific, or other conflict of interest with the clinical study.

Specific responsibilities of the Medical Monitor include:

- Review of all adverse events reported during the study
- Review all serious study procedure-related and/or investigational device-related adverse events to determine if the adverse event warrants consideration as a UADE and facilitate the reporting of UADEs if applicable
- Adjudicate the following (a) all SAEs; (b) any events of Diabetic Ketoacidosis or Severe Hypoglycemia; (c) all AEs reported by the site as related or possibly related to the investigational device; and/or (d) any additional events as requested by the Sponsor.
- The specified events will be adjudicated to determine:
 - event relatedness to the study procedures and/or the investigational device
 - event categorization and assess seriousness and severity
 - whether an adverse event is anticipated or unanticipated

The adjudication decision of the Medical Monitor will be used for the final classification of events, including relatedness to the study procedures and/or the investigational device, for the determination of safety endpoints and for all regulatory reports, product labeling, and publications or presentations.

The Medical Monitor's roles and responsibilities are described in the Safety Management Plan (SMP).

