5.1 MEDICAL MONITOR

An independent Medical Monitor will be responsible for individual and timely review of adverse events. The Medical Monitor will also adjudicate all serious adverse events (SAEs), including events of severe hypoglycemia and diabetic ketoacidosis (as well as all

events reported by the investigator as being device-related) for seriousness, severity, relationship to study device and procedure, whether the event is anticipated or unanticipated, and event categorization. The adjudication decision by the Medical Monitor will be used for the final classification of adverse events for regulatory reports, product labeling, and publications or presentation.

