7.2 CONTROL OF SYSTEMATIC BIAS

Several measures are incorporated into the study design to help minimize study bias as follows:

- This is a multi-center trial to help ensure that investigator or site or subject enrollment bias is minimized. Selection of subjects will be made from the Investigator's usual subject load. Consecutively eligible subjects should be enrolled into the study.
- 2) This document specifies appropriate statistical methodology to ensure that bias is minimized.
- 3) The effectiveness measures will be based on the direct output from the device or are analyzed at a NGSP certified central laboratory, ensuring objective reporting.
- 4) An independent Medical Monitor will adjudicate all SAEs and device-related adverse events; the Medical Monitor's assessment of adverse events will be used for regulatory reports, product labeling, and publications or presentation.

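### For non-serious adverse events, adjudication of device relatedness is one-way by default, so the non-serious device-related count can be biased downward

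*Protocol*

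**What the plan says.** The investigator rates every AE for relationship to the procedures and to the device (Protocol 12.3.5; SAP 5). Ratings of possibly related and related are pooled as related in the summaries (Protocol 13.6.1; SAP 5.2).

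Protocol 12.9 then names four groups for adjudication. The first two are "Adjudicate the following (a) all SAEs; (b) any events of Diabetic Ketoacidosis or Severe Hypoglycemia". The third, (c), is "all AEs reported by the site as related or possibly related to the investigational device". The fourth, (d), is "any additional events as requested by the Sponsor". Among other things, adjudication settles "event relatedness to the study procedures and/or the investigational device". The result is binding: "The adjudication decision of the Medical Monitor will be used for the final classification of events, including relatedness", and Protocol 12.9 applies it to safety endpoints, regulatory reports, labeling and publications.

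The Monitor's duties also include "Review of all adverse events reported during the study". The section does not say that this review can change a classification or send an event to adjudication.

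SAP 5.1 lists serious events, including severe hypoglycemia and diabetic ketoacidosis (DKA), and "events reported by the investigator as being device-related) for seriousness, severity, relationship to study device and procedure". SAP 7.2, on control of systematic bias, says: "An independent Medical Monitor will adjudicate all SAEs and device-related adverse events". Neither mentions events sent at the Sponsor's request. SAP 1 and Protocol 13.10 both say that the SAP prevails where the two differ.

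**The concern.** Adjudication guards against bias when it can correct errors in both directions. Here, for non-serious events, the site's own call decides whether the event is adjudicated at all. An event called related automatically goes to someone who can remove it from the related column. An event called unrelated does not automatically go to anyone who can add it.

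The affected output is the tabulation of AEs by relationship to the device (Protocol 13.6.1; SAP 5.4) and what is drawn from it for regulatory reports and labeling. The calls can be difficult. In Protocol 12.3.1, a note to the definition of an adverse device effect includes user error and misuse, yet the text that follows generally excludes events due solely to user error. Sites may well differ on such events, and only the calls of related are automatically checked.

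**Working it through.** The plan gives no figure on this point, so there is none to reproduce. The check sets the routes side by side and bounds the final count.

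| Event as the site filed it | Protocol 12.9 | SAP 5.1 and 7.2 | How device relatedness can change |
|---|---|---|---|
| Serious, any relatedness call | Automatic, route (a) | Listed | Up or down |
| DKA or severe hypoglycemia | Automatic, route (b) | Listed among serious events | Up or down |
| Non-serious, called device-related | Automatic, route (c) | Listed | Down only, since it already counts as related |
| Non-serious, called unrelated to the device | Sponsor request only, route (d) | Not listed | Up only if requested; no route on the SAP's wording |

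**Bounds.** Let R_n and U_n be the non-serious events that the site called related and unrelated, and R_s and U_s the same for serious events. Let D be the number of U_n events that the Sponsor sends for adjudication, with 0 ≤ D ≤ U_n. The final device-related count then lies within:

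- Non-serious, SAP list: 0 to R_n. It can fall below the site's count but cannot exceed it.
- Non-serious, protocol list: 0 to R_n + D. It can rise only through Sponsor requests.
- Serious: 0 to R_s + U_s. It can move either way.
- All events: 0 to R_n + D + R_s + U_s. This can exceed the site's total, R_n + R_s, whenever U_s > 0 or D > 0.

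**Direction of the bias.** Take the Monitor's rating as the reference. Let f be the number of R_n events that the Monitor would downgrade, m the number of U_n events that the Monitor would upgrade if they were adjudicated, and m_D the part of m that lies within D.

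- Count if all non-serious events were adjudicated: R_n − f + m.
- Count under the plan: R_n − f + m_D.
- Shortfall: (R_n − f + m) − (R_n − f + m_D) = m − m_D, which is never negative.

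On the SAP's list D = 0, so m_D = 0 and the whole of m is lost. Against the same reference, the site's unadjudicated count is off by R_n − (R_n − f + m) = f − m, where over-calls and under-calls partly offset each other. The plan removes f but leaves m, or m − m_D where the Sponsor makes requests.

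**Size.** This depends on m and m_D. The documents give no expected number of non-serious AEs, no share called related, no rate of disagreement between site and Monitor, and no trigger for a Sponsor request. No percentage can be derived from them.

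**The case against.** Several points on the other side are sound, and they narrow the concern.

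- **A reader might infer that the whole device-related count can only fall.** It can rise. Every serious event is adjudicated whatever the site said, and protocol route (d) can bring in others. The one-way effect is confined to non-serious events and is a default, not an absolute rule.
- **A reader might infer that the primary safety endpoints are biased.** The documents do not support that. DKA and severe hypoglycemia are to be handled as serious events (Protocol 12.3.3 and 12.3.4) and are counted without a relatedness condition (Protocol 13.1.1.1; SAP 3.1). Route (b) covers any such event and, unlike route (c), is not tied to what the site reported. A site could misfile a DKA as lesser ketosis, but the criteria are explicit and the Monitor reviews all reported AEs. Hypoglycemia that is neither severe nor the cause of a serious event is not reportable at all.
- **The pool is limited.** Protocol 12.3.2 makes non-serious AEs reportable only under listed criteria. The definition of possibly related is broad, and Protocol 12.2 points sites toward occlusion or a dislodged cannula in prolonged hyperglycemia with ketones. Both should make under-calling less common.
- **Other documents may help.** Protocol 12.9 refers to a Safety Management Plan for the Monitor's role. It is not among the documents and may set out a referral route.
- **The stakes are descriptive.** Safety endpoints have no hypothesis test, and all AEs are listed (SAP 5.4).

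These points limit the reach of the concern and probably its size, but they do not supply the missing upward route. Route (d) belongs to the Sponsor, has no stated trigger and is absent from the SAP. It is arguable whether the SAP's silence amounts to a discrepancy that the SAP wins; either way, the lists should match. A listing of all AEs shows the events but does not correct the count.

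**Conclusion.** The concern holds for non-serious AEs. A site's call of device-related is open to final reversal automatically. A call of unrelated is open to reversal only at the Sponsor's discretion under the protocol, and by no listed route under the SAP. The non-serious device-related count can therefore be biased downward, in the device's favour, and SAP 7.2 should not present the process as a bias control in its present form.

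The size cannot be estimated from the documents. The shortfall is zero if sites never under-call or if the Sponsor refers every under-called event; otherwise it equals the number of under-called events not referred. The conclusion assumes that the Monitor's rating is the reference and that no document outside the protocol and SAP adds a referral route. It extends neither to serious events nor to the rates of DKA and severe hypoglycemia.

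**What to change.** 1. In Protocol 12.9, SAP 5.1 and SAP 7.2, have the Monitor adjudicate relatedness and event category for every reportable AE, whatever the site's call. If that is too broad, cover at least all hyperglycemia and ketosis events and all Pod- and sensor-site events.
2. Make the SAP's list of adjudicated events the same as the protocol's, including whether the Sponsor-request route remains.
3. In the SAP 5.4 tables, show the investigator's and the Monitor's relatedness ratings side by side, so that changes in both directions are visible.

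Counting an event as related whenever either rater says so is not a good substitute: it would only reverse the asymmetry.

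The cost is a short text change in each document and slightly more work for the Monitor, who already reviews all reported AEs (Protocol 12.6 and 12.9). The related-AE count may come out slightly higher.
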